# **Adverse Event recording**

As this is a trial is conducted in critically ill patients with life-threatening sepsis then adverse events are expected to occur regularly in most, if not all, patients. Therefore, unless an adverse event is assessed to meet Serious Adverse Event criteria, these adverse events will not be reported in the case report form and simply noted in the patient's local medical record.

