# **Secondary Endpoints**

- Duration of mechanical ventilation, vasopressor use, renal replacement therapy during index hospital admission up to 90 days
- Length of stay in ICU and hospital up to 90 days
- Antibiotic use (defined daily doses per 1000 occupied bed days and antibiotic-free days) during index hospital admission up to 28 days
- Infection relapse / recurrence or secondary infection requiring further antibiotic treatment during index hospital admission up to 28 days
- Adverse events and adverse drug reactions (including antibiotic related adverse events) during index hospital admission up to 28 days
- Health-related Quality of Life (EQ-5D-5L) and cognitive function (MoCA-Blind) at 6 months
- 1-year mortality
- Incremental costs per Quality-Adjusted Life Year (QALY), and Incremental Net monetary Benefits (INB)

Sponsor: Imperial College London

Version 1.1 22-Aug-2023

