#### 5.6.3 GM-CSF

Intervention / control – GM-CSF (sargramostim) / placebo

In the subset of patients requiring mechanical ventilation, or with two or more organ failures and with persistent lymphopaenia (defined as an absolute lymphocyte count <1.2 x10^9/L on two consecutive calendar days at least 12 hours apart, with no values >1.2 x10^9/L in between) subcutaneous GM-CSF (sargramostim) or a matching placebo will be given.

The dose will be 500µg (two vials) for patients ≥50kg, and 250µg (one vial) for patients <50kg, once a day for 8 days in the ICU.

If the patient is discharged from the ICU before the 8th day then the study drug should be given on the ward until 8 doses in total have been, if logistics allow. It will not be a protocol deviation if this is not possible. If the patient is discharged hospital before the 8th day then the study drug will stop.

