# **Abnormal Laboratory Test Results**

Similarly due to the nature of the underlying critical illness, abnormal laboratory test results will be expected to occur daily for most, if not all, patients whilst in the ICU and therefore do not need to be reported as an AE/AR in the CRF. They will be recorded in the patients' medical record. Any clinically important abnormal laboratory tests will be repeated at appropriate intervals until they return either to baseline or to a level deemed acceptable by the local investigator.

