# Reporting of SAEs

As the primary outcome of the trial includes mortality, then death does not require reporting as an SAE unless, in the opinion of the local PI, the death was attributable to a study intervention / IMP or the trial protocol.

Similarly, the secondary outcomes have been selected to capture the most commonly occurring safety events in critically ill patients (e.g. organ failure and support, and new infection, including Confidential 36

Sponsor: Imperial College London

Version 1.1 22-Aug-2023

Clostridium Difficile infection). Therefore, any events that are captured as an outcome in the eCRF do not require reporting as an SAE unless in the opinion of the local PI the event was attributable to a study intervention / IMP or the trial protocol.

Rapid reporting of all SAEs i.e. within 24 hours, occurring during the patient's ICU stay up to a maximum of 28 days must be performed as detailed in the study-specific safety reporting instructions.

Active monitoring of participants after discharge from ICU or after 28 days is not required, but if the investigator becomes aware of safety information that appears to be drug or trial related, involving a participant who participated in the study, even after an individual participant has completed the study, this should be reported to the Sponsor.

All SAEs will be reviewed by the Chief Investigator or a designated medically qualified representative to confirm expectedness and causality.

Reporting of SAEs and review by the CI will be via the trial data collection system (CRF/eCRF)

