#### **Database**

Trial data will be collected on an electronic case report form (eCRF). Data will be entered via web-based database through electronic data capture (EDC). The database used to capture this information is the OpenClinica database. Data is entered into the database by the site team. The database will raise automatic queries and allow manual queries to also be raised which will be checked and validated by the Trial Manager and Monitor. All data, changes to data and query resolution will be included in an audit trail including dates. Specific instructions on how to enter data including drug naming and deal with queries are detailed in the eCRF completion guide. Automated Randomisation will be carried out using the OpenClinica system in accordance with ICTU specific SOPs.

Adverse events will be captured in the eCRF and all Serious Adverse Events will require sign off by the Principal Investigator at the site.

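### The adverse event endpoint (hospital stay to day 28) is wider than the safety data collected, and SAE comparisons by arm depend on ICU stay

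*Protocol*

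**What the plan says.** Section 3 (Secondary Endpoints) and the Trial Summary list as an endpoint "Adverse events and adverse drug reactions (including antibiotic related adverse events) during index hospital admission up to 28 days". It is not limited to serious events or to the ICU.

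The collection rules are these:

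- Section 8, Adverse Event recording: "unless an adverse event is assessed to meet Serious Adverse Event criteria, these adverse events will not be reported in the case report form". Such events are noted only in the local medical record.
- Section 8, Abnormal Laboratory Test Results: these "do not need to be reported as an AE/AR in the CRF".
- Section 8, Reporting of SAEs: rapid reporting of SAEs occurring during the "ICU stay up to a maximum of 28 days must be performed". The same section adds: "Active monitoring of participants after discharge from ICU or after 28 days is not required". A duty to report to the Sponsor remains "if the investigator becomes aware of safety information that appears to be drug or trial related". Events already captured as outcomes in the eCRF are exempt from SAE reporting unless judged attributable to an intervention, the IMP or the protocol.
- Section 12, Database: "Adverse events will be captured in the eCRF".
- Section 6, Visit Schedule: daily clinical data are collected to day 28 only while the patient is in ICU, with a final hospital data collection at discharge, up to day 90.
- Section 9, Analysis of secondary outcomes: SAEs are tabulated and modelled, with odds ratios and incidence rate ratios. No analysis of non-serious events or reactions is described.

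On where study drug is given, the GM-CSF text (numbered 5.6.3) says that after ICU discharge the "study drug should be given on the ward until 8 doses in total have been, if logistics allow". The opening of the Treatment part of Section 6 confines trial treatments to the ICU.

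**The concern.** The endpoint promises more than the case report form will hold, in seriousness and in time window. This cannot be left to the SAP, because no analysis can recover events that were not collected.

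Three things are at stake.

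- **Reactions to study treatment.** Part of the diagnostic trial's rationale in Section 2 is that stopping unnecessary antibiotics avoids their side effects. Non-serious antibiotic reactions are in the endpoint but do not reach the CRF unless they are collected as another outcome.
- **Ward dosing.** GM-CSF or placebo may be given on ward days on which active SAE monitoring is not required. The product is not licensed in the UK for any indication (Section 7).
- **Comparability of arms.** Mandatory SAE observation ends at ICU discharge. Discharge happens after randomisation and may be affected by treatment; ICU length of stay is itself a secondary endpoint. The arm discharged earlier is watched for less time, so its SAE count can be lower with no difference in risk.

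**Working it through.** The protocol states no figure to reproduce. The check is a comparison of texts, followed by a bound on the observation-time effect.

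**1. Endpoint against collection**

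| Component of the endpoint | Systematically collected? |
|---|---|
| SAEs in ICU to day 28 | Yes (Section 8) |
| New infection including C. difficile, hospital stay to day 28 | Yes, as an outcome (Sections 3 and 8) |
| Organ support, hospital stay to day 90 | Yes, as an outcome (Sections 3 and 8) |
| Other non-serious events and reactions, in ICU or on the ward | No |
| Other SAEs on the ward before day 28 | No; passive reporting only, if apparently drug or trial related |

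The last two rows are inside the endpoint and outside collection. The Database sentence in Section 12 would fill part of the gap if read literally, but it contradicts the specific recording rule in Section 8.

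**2. How far ward dosing can reach**

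Entry to the GM-CSF trial is allowed up to 120 hours (5 days) after ICU admission (Section 5, additional exclusion criteria), with 8 once-daily doses. If the first dose is given on day 5, the eighth falls on day 5 + 7 = 12 after ICU admission. If it is given a day later, the eighth falls on day 13. A patient who leaves ICU before then can receive study drug during the ward period without active SAE monitoring.

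**3. Size of the observation-time effect**

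Let the daily SAE rate λ be constant and equal in both arms, the control mean ICU stay be L days, and the intervention arm's stay be d days shorter.

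- Expected SAEs per patient: λL in control and λ(L − d) in the intervention arm.
- Apparent reduction: 1 − (L − d)/L = d/L.
- Rate ratio with ICU days as exposure: λ/λ = 1.

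For d, the only ICU-stay effect given in the protocol is the meta-analysis in Section 2 of conservative fluid management or de-resuscitation, in its whole critically ill population: 1.88 days shorter, 95% CI 0.12 to 3.64. The protocol gives no mean ICU stay, so L = 8 to 12 days is an assumption.

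| d (days) | L = 12 | L = 8 |
|---|---|---|
| 0.12 | 0.12/12 = 1.0% | 0.12/8 = 1.5% |
| 3.64 | 3.64/12 = 30.3% | 3.64/8 = 45.5% |

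The apparent reduction therefore runs from about 1% to about 45%. The proportion with at least one SAE, and hence an odds ratio, moves in the same direction, because fewer days at risk give fewer patients an event. A rate with ICU time as the exposure returns 1 under these assumptions. Section 9 does not state the exposure term for its incidence rate ratios.

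**The case against.** The case for the protocol has substance.

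- **Limiting non-serious recording is reasoned.** Section 8 explains that adverse events are expected in most, if not all, patients in this setting. That stands as a reason not to record them. It does not support keeping an endpoint that needs them.
- **Capture does not cease at ICU discharge.** A reader might infer that nothing is recorded afterwards, or that no antibiotic-related events are captured at all. The documents do not support this. Apparently drug- or trial-related information must still be reported if the investigator learns of it. New infection, including C. difficile, and organ support are outcomes with hospital-wide windows. Serious antibiotic reactions in ICU are SAEs, and the definition of serious extends to important events that may jeopardise a patient. Passive reporting is selective, however, and cannot give comparable counts by arm.
- **The analysis may remove the artefact.** Section 9 includes incidence rate ratios. If ICU time is the exposure, equal daily rates give a ratio of 1, and that detail may properly sit in the SAP. The odds ratios planned alongside remain affected.
- **A single percentage would not be safe.** A reader might combine the 1.88-day point estimate with an assumed stay and quote one figure for the artefact. That estimate comes from the whole meta-analysis population rather than the sepsis studies, against liberal or standard care, with a wide interval. It concerns fluids only; nothing in the protocol quantifies an ICU-stay effect for diagnostics or GM-CSF. If SAE rates are lower late in the stay, the deficit is smaller.
- **The Database sentence is general**, and the specific rule in Section 8 probably governs. It is a wording conflict, though still worth removing.
- **Other documents are not shown.** The safety reporting instructions and the study manual may add detail, but the protocol's own rules set the narrower scope.

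**Conclusion.** The mismatch is established from the protocol alone and needs no assumption. The endpoint covers serious and non-serious events and reactions, in ICU and on the ward, to day 28. Systematic collection covers SAEs in ICU plus the safety events captured as outcomes. Non-serious reactions not collected as outcomes, and most ward SAEs, including those on ward dosing days, fall outside it. As worded, the endpoint cannot be derived.

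The dependence of SAE counts and odds ratios on ICU stay follows from the reporting window. Its direction is clear wherever treatment changes ICU stay and daily risks are equal. Its size is not fixed by the documents: about 1% to 45% holds only for a 0.12 to 3.64 day difference, an assumed mean stay of 8 to 12 days and a constant daily SAE rate.

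This should be fixed. It concerns one secondary endpoint and the safety comparison, and leaves estimation of the primary outcome untouched.

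**What to change.** Choose one of two routes.

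1. **Narrow the endpoint.** In Section 3 and the Trial Summary, restrict it to SAEs in ICU up to day 28 plus the safety events captured as outcomes. In Section 9, make the between-arm SAE comparison a rate with ICU time at risk as exposure, treating death and ICU discharge as competing events, in place of odds ratios. The cost is a text amendment and no new data. The downside is that ward events, including those on ward dosing days, stay outside systematic comparison.
2. **Widen the collection.** Collect SAEs in all arms over one window, from randomisation to hospital discharge or day 28, ward dosing days included, at the discharge data collection already in the Visit Schedule. Add a short eCRF list of the antibiotic- and GM-CSF-related reactions that the endpoint needs. The cost is a protocol amendment, a small eCRF change and some ward chart review.

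Under either route, reconcile Adverse Event recording, Reporting of SAEs, Analysis of secondary outcomes and Database, so that they describe the same events over the same period. Separately, reconcile the opening of Treatment in Section 6 with the GM-CSF text on where study treatment is given.

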# **Abnormal Laboratory Test Results**

Similarly due to the nature of the underlying critical illness, abnormal laboratory test results will be expected to occur daily for most, if not all, patients whilst in the ICU and therefore do not need to be reported as an AE/AR in the CRF. They will be recorded in the patients' medical record. Any clinically important abnormal laboratory tests will be repeated at appropriate intervals until they return either to baseline or to a level deemed acceptable by the local investigator.

# Serious Adverse Events (SAE)

#### **Definition of SAE**

An SAE is defined as any event that

- Results in death;
- Is life-threatening\*;
- Requires hospitalisation or prolongation of existing inpatient's hospitalisation\*\*;
- Results in persistent or significant disability or incapacity;
- Is a congenital abnormality or birth defect;
- \* "Life-threatening" in the definition of "serious" refers to an event in which the participant was at risk of death at the time of the event; it does not refer to an event which hypothetically might have caused death if it were more severe.
- \*\* "Hospitalisation" means any unexpected admission to a hospital department. It does not usually apply to scheduled admissions that were planned before study inclusion or visits to the emergency department (without admission).

Medical judgement should be exercised in deciding whether an adverse event/reaction is serious in other situations. Important adverse events/reactions that are not immediately life-threatening, or do not result in death or hospitalisation but may jeopardise a subject, or may require intervention to prevent one of the other outcomes listed in the definition above should also be considered serious.

# Reporting of SAEs

As the primary outcome of the trial includes mortality, then death does not require reporting as an SAE unless, in the opinion of the local PI, the death was attributable to a study intervention / IMP or the trial protocol.

Similarly, the secondary outcomes have been selected to capture the most commonly occurring safety events in critically ill patients (e.g. organ failure and support, and new infection, including Confidential 36

Sponsor: Imperial College London

Version 1.1 22-Aug-2023

Clostridium Difficile infection). Therefore, any events that are captured as an outcome in the eCRF do not require reporting as an SAE unless in the opinion of the local PI the event was attributable to a study intervention / IMP or the trial protocol.

Rapid reporting of all SAEs i.e. within 24 hours, occurring during the patient's ICU stay up to a maximum of 28 days must be performed as detailed in the study-specific safety reporting instructions.

Active monitoring of participants after discharge from ICU or after 28 days is not required, but if the investigator becomes aware of safety information that appears to be drug or trial related, involving a participant who participated in the study, even after an individual participant has completed the study, this should be reported to the Sponsor.

All SAEs will be reviewed by the Chief Investigator or a designated medically qualified representative to confirm expectedness and causality.

Reporting of SAEs and review by the CI will be via the trial data collection system (CRF/eCRF)

### **Definition of a Serious Adverse Reaction (SAR)**

A SAR is defined as a SAE that is judged to be (possibly, probably or definitely) related to any dose of study drug administered to the participant.

### **Definition of Suspected Unexpected Serious Adverse Reaction (SUSAR)**

Any SAR that is NOT consistent with the applicable product information as set out in the Reference Safety Information (RSI) section of the Investigator Brochure (IB) or Summary of Product Characteristics (SmPC).

### Reporting of SUSARs

SUSARs should be notified to the appropriate regulatory authority, the relevant REC and the Sponsor in accordance with regulatory requirements. SUSARs which are fatal or life-threatening will be reported not later than seven days after alerting the sponsor to the reaction. Any additional relevant information will be sent within eight days of the report.

A SUSAR which is not fatal or life-threatening will be reported within 15 days of first knowledge by the sponsor. The sponsor will inform all investigators about SUSARs occurring in the study.

Follow up of participants who have experienced a SUSAR should continue until recovery is complete or the condition has stabilised.

SUSAR reports will be unblinded prior to submission if required by national regulatory requirements.

#### **Developmental Safety Update Reports / Annual Safety Reports**

Developmental Safety Update Reports (DSUR) / Annual Safety reports will be submitted to the Sponsor, the Ethics Committee and Regulatory Authority in accordance with local / national regulatory requirements.

Sponsor: Imperial College London

Version 1.1 22-Aug-2023

### **Pregnancy**

GM-CSF is not approved in pregnancy and is an exclusion criterion for this intervention. Due to the life-threatening illness at the time of recruitment, pregnancy is not expected to occur. Should it occur pregnancy is not considered an SAE but should be recorded and followed up to ensure a congenital abnormality does not occur.

### Reporting urgent safety measures

If any urgent safety measures are taken the CI/Sponsor shall immediately and in any event no later than three days from the date the measures are taken, give written notice to the MHRA and the relevant REC of the measures taken and the circumstances giving rise to those measures.

#### 9. STATISTICAL ANALYSES

### Sample Size and power considerations

The sample size has been calculated based on 90-day mortality. To increase the power of the trial the primary outcome will include both 90-day mortality and clinical state (in-hospital without organ support, in-ICU with organ support, discharged) over 90 days. Simulations to further examine the power of the study under a range of conservative outcomes on the primary outcome with clinical state included have been performed on the planned trial sample size based on mortality alone.

The initial calculation used data from the ICNARC Case Mix Programme which reported a mortality rate of 31.8% for all sepsis admissions to ICU.(43) Allowing for the trial exclusion criteria we anticipate a 30% mortality rate in the standard of care arm.

In the diagnostic and fluid trials we aim to recruit 3758 patients to both trials. This is based on a clinically important target difference in mortality of 5%. Assuming 30% mortality, 5% reduction, 90% power, 5% two-sided type I error we will require 1674 per arm. We then inflate by 10% for a potential interaction effect between the intervention arms, and 2% to account for loss to follow-up.

The high-risk subset (35% eligibility for GM-CSF) will have a higher control mortality rate.(43-45) We assume a 45% mortality rate in the standard of care arm. Our meta-analysis for GM-CSF in sepsis trials demonstrated a relative risk for mortality of 0.74 (95%CI 0.49-1.14). We aim to recruit 1300 participants which will provide 90% power to detect 9% difference in mortality with type I two-sided error or 5%, and factoring in approximately 2% loss to follow up.

No adjustments for multiple comparisons have been made for these three trials as the comparisons are three distinct treatments where each result will provide a separate conclusion. (46)

In addition, we have undertaken simulations to further examine the power of the primary analysis of 90-day mortality and clinical states (in-hospital without organ support, in-hospital with organ support, discharged) for the antibiotic and fluid trials, assuming a more conservative reduction in mortality. Treating clinical state as an ordinal outcome which is repeatably observed over time increases statistical efficacy because it makes the most of all the information available. We define clinical status as an ordinal outcome with three passing states and one absorbing state.

Clinical status is categorised as:

1. Discharged from hospital

Sponsor: Imperial College London

Version 1.1 22-Aug-2023

- 2. In-hospital without Organ Support
- 3. In-ICU with Organ Support
- 4. Death (absorbing state i.e. cannot transition out of this state)

Using data from the VANISH and LeoPARDS trials (44, 47) we estimated the proportion in each clinical state on days 0, 7, 14, 28 and 90 days in the standard of care arm (Table 2).

Sponsor: Imperial College London

Version 1.1 22-Aug-2023

Table 2: The anticipated probability of each clinical state over the first 90 days in the standard of care arm

State	0	7	14	28	90
1 = Discharge	0.00	0.06	0.21	0.42	0.60
2 = Hospital without support	0.15	0.48	0.32	0.17	0.05
3 = ICU with support	0.85	0.41	0.29	0.14	0.05
4 = Death	0.00	0.05	0.18	0.27	0.30

Simulations then estimated power for the new treatment under five scenarios, under which mortality reduction in the treatment arm was always kept at 3%, whereas the proportion transitioning to a better (lower) clinical state changed in each scenario, as shown in Table 3. Data for each simulation was generated using a Markov transition model. First, at least two sets of State Transition Probabilities (STP) corresponding to each timepoint and each scenario were estimated, using iterative methods to minimise the difference between the target clinical state probabilities and those derived from the STPs. Then, for each set of STPs, random draws of a standard (0,1) uniform distribution for each individual and timepoint were mapped onto the discrete clinical states by partitioning the interval [0,1] into sub-intervals with widths corresponding to the STPs. These simulations were analysed using a mixed effects proportional odds model which included the discrete timepoints, binary treatment variable and interactions between them as fixed effects, and participant as a random effect. In total 300 simulations were analysed for each scenario. The power was calculated based on the proportion of simulations from a two-sided hypothesis where the 95% confidence interval excluded the value of no difference (i.e. OR = 1).

Since the STPs used only imprecisely replicated the target probabilities, a slightly different power estimate was obtained for each scenario depending on which STPs were used. The final power estimate for each scenario was derived by fitting an approximate linear relationship between the 90-day change in mortality and the power as the STPs varied, and identifying the level of power corresponding to a 3% mortality reduction.

Table 3: Scenarios examining differing percentage change in clinical state achieved by day 90 in the intervention arm relative to the control arm

Scenario	Discharged	Hospital without support	Hospital with support	Mortality	Power
	Change (%)	Change (%)	Change (%)	Change (%)	
1	+ 1	+ 1	+ 1	-3	0.60
2	+ 1	+ 2	+ 0	-3	0.57
3	+ 1	+ 3	-1	-3	0.75
4	+ 3	+ 1	-1	-3	0.83
5	+ 4	+ 1	-2	-3	0.88

Sponsor: Imperial College London

Version 1.1 22-Aug-2023

The power of the trial based on the simulation scenarios can be seen in final column of Table 3. The simulations have demonstrated that the trial will have good power under scenarios 3, 4 and 5 with power of 75%, 83% and 88% respectively. In summary the trial will have good power to detect a treatment difference when a minimal clinically important change in mortality of 3% by 90 days is combined with a reduction of 1% or more in participants with organ support in ICU by 90 days, and an increase of 3% or more participants to either in-hospital without support or discharge by 90 days.

